the suprapubic area in the bilateral lower quadrants (as shown in the figure at right). The program that will be used is a high frequency (80Hz) program that runs for an hour in duration. It will be initiated 5 minutes prior to speculum placement. Participants will be instructed to increase the amplitude of the current as needed to provide analgesia but avoiding discomfort from the TENS stimulation. All participants will receive a paracervical block of 20mL 1% lidocaine with sodium bicarbonate followed by rigid dilation and dilator placement per standard cervical preparation protocol. Participants will complete 100mm VAS immediately following dilator placement. VAS is a 100mm line on sheet of paper with 0 being no pain and 100mm being worst pain of their life. The number of dilators, type of dilators, and use of adjunctive mifepristone/misoprostol will be according to providers' clinical judgement. Dilator placement will be performed by either Family Planning Fellow, PGY-3 OB/GYN resident, or Nurse Practitioner. All participants will receive prescriptions for twenty tablets of ibuprofen (600mg) and twelve tablets of hydrocodone/acetaminophen 5/325, which is the standard post-dilator insertion pain protocol for this clinic site. Participants will be allowed to leave prior to the end of the initial one-hour program. They will be sent home with instructions of how to run the TENS unit as needed for pain control.

Following the initial hour of use patients can re-activate the TENS unit as often as desired, using the same program. Participants will be given a log to record when TENS unit was used and whether additional pain medications were taken (attached). They will return their completed log and bring pill bottles on the day of surgery to confirm medications used.

Of note, in our practice a second set of cervical dilators is often placed 6 hours after first set in patients over 20 weeks gestation. During this placement the first set is removed, further rigid dilation is performed, and new dilators are placed per standard cervical preparation protocol. Pain score on 100mm VAS will be recorded following this dilator placement as well as a secondary outcome. Participants will run the TENS unit in the same manner as the initial dilator placement for dilator exchange.

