On the day of surgery participants will record their highest interval pain score on 100mm VAS. They will also be asked their satisfaction with the TENS device. The TENS unit will be returned on the day of surgery.

The investigative procedures in this study are as follows:

- 100mm VAS immediately following dilator placement
- 100mm VAS immediately following dilator exchange (if applicable)
- 100mm VAS in the preoperative area rating highest pain level in the interval between dilator placement and surgery
- Log detailing when pain was felt in pre-operative interval period, TENS use or nonuse, and use or nonuse of adjunctive pain medication
- 5 Point Likert Scale determining patient satisfaction with TENS (attached)
- Demographic information sheet (attached)

VAS scoring and Log details will be completed on paper. Likert scale and demographics will be collected on tablets.

There are no plans for long-term follow up.

STU#:

DATA AND SPECIMEN BANKING

No data or specimens will be banked for future use.

SHARING RESULTS WITH PARTICIPANTS

Study results will be shared with the participants upon request. This request can be made at any point within the study time period.

Study results will be disseminated within the medical community via scientific publication in a peer-reviewed journal once study completion, data analysis, and manuscript approval has been achieved.

STUDY TIMELINES

The study will begin in March 2019 with participant recruitment. It is anticipated, based on a typical clinic volume of 400 patients requiring osmotic dilator placement prior to dilation and evacuation, that recruitment will take 12 months. Primary data analyses will then take place over the next two months, with plan to complete analyses by May 2019. Manuscript preparation, submission, and approval/publication will then occur.

An individual's participation in the study will be for no longer than 48 hours, which is the maximum amount of time between dilator placement and dilation and evacuation procedure. No further follow up will be required by the patient.

INCLUSION AND EXCLUSION CRITERIA

Inclusion Criteria:

1. Women \geq 18 years of age
2. Gestational age between 14 weeks and 23 weeks 6 days
3. Willing and able to sign an informed consent in English
4. No contraindications to TENS

Exclusion criteria

1. Incarceration
2. Preterm Premature Rupture of Membranes or evidence of intra-amniotic infection
3. Presence of implanted cardiac device

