4. Lack of sensation to touch on area of electrode placement
5. Prior TENS use
6. Opioid dependence

All patients between 14 weeks and 23 weeks 6 days gestation who schedule an appointment for a Dilation and Evacuation procedure with Northwestern Family Planning will be reviewed for study eligibility by the study team. All patients will be asked by clinical staff when scheduling an appointment if they have an implanted cardiac device or have used a TENS unit in the past. If eligibility criteria are met, then the patient will be approached regarding this study during the initial consultation appointment following description of dilator insertion procedure.

VULNERABLE POPULATIONS

The population being studied is pregnant women who have previously decided to have a termination of pregnancy or have an intrauterine fetal demise. They will confirm their decision for termination and consent to the termination procedure prior to being approached for study participation and subsequent TENS unit placement. TENS units have previously been studied

STU#:

during labor without adverse effects on the fetus. Therefore, the only potential risk would be patient discomfort from the TENS or allergic reaction to the electrode pads. These risks are rare and short-lived. Any fetal risk that has not previously been identified would be insignificant, as termination of pregnancy will occur 24-36 hours later.

PARTICIPANT POPULATION(S)

Accrual Number:	Category/Group: (Adults/Children Special/Vulnerable Populations)	Consented: Maximum Number to be Consented or Reviewed/Collected/Screened	Enrolled: Number to Complete the Study or Needed to Address the Research Question
Local	Pregnant Women	70	70
Study-wide			
Total:		70	70

RECRUITMENT METHODS

Study participants will be recruited at the Family Planning Clinic at Northwestern Memorial Hospital in Chicago, IL. This study will be registered with ClinicalTrials.gov per protocol. Participation will be completely voluntary. The Family Planning Clinic population is highly variable and includes patients with both Medicaid and private insurance. It includes patients referred from the greater Chicagoland area as well as from nearby states with more prohibitive abortion legislation. This clinic performs about 400 dilation and evacuation procedures requiring dilator placement per year.

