Patients will be approached for informed consent by a study team member following determination of eligibility at the initial clinic termination consultation appointment at the Northwestern University Family Planning Clinic. No outsourced advertising for the study will be done.

COMPENSATION FOR PARTICIPATION IN RESEARCH ACTIVITIES

No compensation will be provided for the patients to participate in this study

WITHDRAWAL OF PARTICIPANTS

Participants may choose to discontinue participation at any time.

A participant would be discontinued from this study if they opted to discontinue the TENS unit prematurely during initial dilator placement or if an unexpected allergy to the electrode pads was noted during initial placement. Participants would be excluded from secondary analyses if they did not complete their pain log or agree to report pain/satisfaction with TENS on day of surgery, but would still be included in the primary analyses.

RISKS TO PARTICIPANTS

STU#:

Minimal risk to participants is anticipated with this study protocol.

The physical risk of this study is that the TENS may create a mildly uncomfortable sensation across the lower abdomen. The study participant will be instructed to increase the intensity of the TENS to provide analgesia without excessive discomfort from the unit, however, some discomfort may be felt for a short period of time as the participant is increasing and decreasing the intensity of the TENS. This discomfort is reversible, however, by decreasing the intensity or discontinuing use of the device. The participant may also have a contact allergic reaction to the electrode pads. This contact allergy is short lived and is easily treated with topical corticosteroids.

POTENTIAL BENEFITS TO PARTICIPANTS

If, as we anticipate, use of TENS improves pain control during dilator insertion, this would provide an inexpensive, non-pharmacologic method of analgesia with few contraindications. This could improve the patient experience during a necessary but extremely uncomfortable part of the abortion process.

DATA MANAGEMENT AND CONFIDENTIALITY

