Data will be managed using REDCap. All data will either be entered directly into REDCap (with data collected on tablet) or will be entered manually by the primary investigator or research assistant. The paper forms and iPads will be stored in a locked cabinet in a locked office only accessible to the primary investigator and research assistant. All paper forms will be shredded in HIPAA bins following data entry.

Study participants will be compared on baseline characteristics using appropriate statistical methods depending on normal distribution (student t-test or chi-squared test) or non-normal distribution. Primary and secondary outcomes will be measured using appropriate statistical analyses for continuous or categorical data. A two-tailed p value of less than or equal to 0.05 will be considered statistically significant.

The number of subjects needed to show a 20mm reduction on VAS with a standard deviation of 30mm is 56, or 28 per arm. To account for subject discontinuation we will attempt to recruit 70 participants.

According to previous studies the minimum clinically significant difference in VAS is 15mm, however, this is within the standard deviation of typical VAS scores of pain during laminaria insertion and could confound study results. Soon et al previously used a 25mm reduction on VAS to calculate power in a previous study examining pain control during dilator insertion using paracervical block. We have chosen to use a 20mm reduction on VAS as this difference has shown significant in previous pain management research studies and we believe this to be a difference that will alter clinician practice patterns.

PROVISIONS TO MONITOR THE DATA TO ENSURE THE SAFETY OF PARTICIPANTS

This study does not involve more than minimal risk to the participants

PROVISIONS TO PROTECT THE PRIVACY INTERESTS OF PARTICIPANTS

On the day of their pre-operative abortion consultation appointment, a study team member will approach eligible patients regarding study enrollment. The questions they are asked regarding

STU#:

personal health information and demographics are questions that would be asked regardless of study participation.

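### The protocol names stimulation discomfort and pad allergy as the device risks, but no described measurement or outcome records either effect, or why a unit was stopped, in either arm

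*Combined protocol and SAP*

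**What the plan says.** - **Risks named.** VULNERABLE POPULATIONS states that "the only potential risk would be patient discomfort from the TENS or allergic reaction to the electrode pads" and calls these risks rare. RISKS TO PARTICIPANTS describes the same two effects. It says that discomfort can be reversed by turning the intensity down or stopping the device, and that a pad allergy is brief and treatable.
- **Discontinuation.** WITHDRAWAL OF PARTICIPANTS lets a participant leave whenever she wishes. The study itself discontinues her in two situations, both tied to initial placement: she stops the unit early, or "if an unexpected allergy to the electrode pads was noted during initial placement".
- **Continued use.** PROCEDURES INVOLVED sends the unit home: "Following the initial hour of use patients can re-activate the TENS unit as often as desired, using the same program". For those who have an exchange, often patients over 20 weeks, "Participants will run the TENS unit in the same manner as the initial dilator placement for dilator exchange".
- **What is measured.** PROCEDURES INVOLVED lists three VAS pain scores, a five-point satisfaction scale, a demographics sheet and a "Log detailing when pain was felt in pre-operative interval period, TENS use or nonuse, and use or nonuse of adjunctive pain medication".
- **Outcomes.** OBJECTIVES and STUDY ENDPOINTS cover pain, time in clinic, adjunctive medication, and acceptability or satisfaction. None is an adverse effect.
- **Monitoring.** The safety-monitoring section is one sentence: "This study does not involve more than minimal risk to the participants".

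**The concern.** A trial that names two device effects in advance should be able to say how often each occurred in each arm. Followed as described, this one cannot do so directly. A skin reaction found at home, or a unit left off because the current was unpleasant, has no field to go into. The gap cannot be closed at analysis: the data would not exist, and the paper forms are shredded after entry, so a stray note that is not entered is lost.

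The planned data are weakest among those who tolerate the device least. A participant who stops at initial placement is discontinued, so she may never reach the satisfaction question on the day of surgery. Those who do not complete the log, or do not report pain and satisfaction, are left out of the secondary analyses. The log shows whether the unit was used, but is not described as showing why it was not.

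There is also a gap in the text. The allergy rule stops at initial placement, while use of the device does not.

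**Working it through.** The plan gives no adverse-effect rate or precision target, so there is no figure of its own to reproduce. The check has two parts.

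**1. Each described instrument against the three facts needed**

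| Instrument | Skin reaction | Device discomfort | Reason for stopping |
|---|---|---|---|
| VAS after placement, after exchange, and highest interval pain | no | no (procedure or interval pain) | no |
| Log: pain, TENS use or nonuse, medication | no | no | no |
| Satisfaction scale | no | indirect | no |
| Demographics sheet | no | no | no |
| Discontinuation at placement | allergy leads to discontinuation; no recording step described | indirect | not described as recorded |

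The log pairs pain with use. Nonuse without pain can therefore be told from nonuse despite pain; only the reason for the latter is missing.

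**2. What systematic recording could show**

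Inputs: 70 participants allocated 1:1 (STUDY ENDPOINTS), so n = 70/2 = 35 per arm; 28 per arm if only the 56 of the power calculation contribute. The true rates p are assumptions.

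- Upper limit with zero events, one-sided 95%: 1 − 0.05^(1/n). For n = 35 this is 8.2%; for n = 28, 10.1%.
- Upper limit with zero events, two-sided exact 95%: 1 − 0.025^(1/n). For n = 35 this is 10.0%; for n = 28, 12.3%.
- Probability of at least one case: 1 − (1 − p)^n.

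| Assumed true rate p | n = 35 | n = 28 |
|---|---|---|
| 1% | 30% | 25% |
| 2% | 51% | 43% |
| 5% | 83% | 76% |
| 10% | 97% | 95% |

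Exact two-sided 95% intervals for small counts out of 35: one event, 0.1% to 14.9%; two events, 0.7% to 19.2%; three events, 1.8% to 23.1%.

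Sham participants wear pads without current (PROCEDURES INVOLVED). Pad reactions can therefore be compared between arms. Discomfort caused by current can arise only in the active arm, and sham answers would show the background level of reporting.

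**The case against.** The strongest reply is that the device is low-risk, participants stay in control of it, and some tolerability information is already planned. Much of this stands, and it rules out several stronger readings.

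- **A reader might infer that the two risks are acted on only at initial placement.** That is true only of the study-driven discontinuation rules. The right to withdraw (WITHDRAWAL OF PARTICIPANTS, CONSENT PROCESS) and the advice on discomfort and allergy (RISKS TO PARTICIPANTS) carry no time limit.
- **A reader might infer that nothing can be said about tolerability by arm.** Satisfaction, use and nonuse, and discontinuations at placement can each be tabulated by arm. What is missing is a direct measure.
- **A reader might see a contradiction between** "An individual's participation in the study will be for no longer than 48 hours" **and** "as termination of pregnancy will occur 24-36 hours later"**.** The first is a maximum and the second is compatible with a typical interval. Neither is stated as a period of device exposure, which comes in one-hour programs as wanted, and no home-use figure is given.
- **A reader might take the benefit claim of few contraindications as a claim about adverse-event rates.** It concerns who can use the device.
- **The forms are attachments that are not visible here.** The point can rest only on how the protocol describes them. If they already hold these items, the protocol need only say so.
- **At low rates the trial would show little.** At 1% or 2%, 35 participants have only a 30% or 51% chance of showing a case.
- **Asking about stimulation could prompt sham participants to guess their allocation.** This is a fair objection, and it governs where the questions are placed.

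None of this supplies a record of the two named effects.

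**Conclusion.** The point holds as a gap in planned data collection. On the protocol's description, neither named effect, nor the reason for stopping the unit, is measured in either arm, although use goes on at home and at exchange. With recording in all 35 participants of an arm, zero events would support an upper limit of 8.2% (one-sided) or 10.0% (two-sided). Without recording, no such limit can be stated.

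This rests on the described content of forms that cannot be seen, on complete data in 35 per arm, and, for the detection probabilities, on assumed rates. The primary outcome, its analysis and the sample size are unaffected, so this is a cheap improvement and not a threat to the main result. Separately, the discontinuation rule and the text on continued use need to be reconciled.

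**What to change.** Add three fixed items to the existing day-of-surgery tablet form, worded identically in both arms and placed after the interval VAS and the satisfaction rating:

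1. skin reaction under the pads (yes/no);
2. discomfort from the device (none/mild/moderate/severe);
3. unit stopped, or not used, because of either.

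Ask the same items when a participant is discontinued at initial placement, since she may not reach the later form. Do not ask the discomfort item at dilator exchange, where it would come before the remaining ratings and could prompt guesses about allocation. Report counts by arm with exact 95% intervals. If the attached forms already contain these items, say so in PROCEDURES INVOLVED.

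Reconcile WITHDRAWAL OF PARTICIPANTS, whose rule names initial placement only, with the continued use at home and at exchange in PROCEDURES INVOLVED. The investigator decides the clinical rule.

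Cost: about one minute per participant and a short wording change, with no extra visit. Some low-grade symptoms will be reported. A small risk of unblinding remains, limited by asking after the other ratings.

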STU#:

PROTOCOL TITLE: Transcutaneous electrical nerve stimulation (TENS) for pain control during cervical dilator placement prior to dilation and evacuation: A randomized controlled trial

PRINCIPAL INVESTIGATOR:

[name], MPH
[name]
[name]
[name]
Department of OB/Gyn
[contact]

VERSION NUMBER:

1

VERSION DATE:

12/4/18

STUDY SUMMARY:

Investigational Agent(s) (Drugs or Devices)	Primera TENS/NMES Unit with HAN Waveform by Chattanooga
IND / IDE / HDE #	
Indicate Special Population(s)	 Children  Children who are wards of the state  Adults Unable to Consent  Cognitively Impaired Adults  Neonates of Uncertain Viability  Pregnant Women  Prisoners (or other detained/paroled individuals)  Students/Employees
Sample Size	70
Funding Source	Society of Family Planning Research Fund
Indicate the type of consent to be obtained	 Written  Verbal/Waiver of Documentation of Informed Consent  Waiver of HIPAA Authorization  Waiver/Alteration of Consent Process
Site	 Lead Site (For A Multiple Site Research Study)  Data Coordinating Center (DCC)
Research Related Radiation Exposure	 Yes  No
DSMB / DMC / IDMC	 Yes  No

STU#:

OBJECTIVES:

- Primary Outcome: Self-reported pain on 100mm VAS immediately following dilator placement
- Secondary Outcomes:
 - Self-reported pain at dilator exchange (if applicable)
 - Amount of time (in minutes) spent in clinic following dilator insertion
 - Self-reported highest level of pain between dilator placement and D&E
 - Number and type of adjunctive pain medications used
 - Patient acceptability

The hypothesis is that use of TENS will decrease pain by 20mm on VAS during initial dilator placement prior to dilation and evacuation, improving patient's overall pain management

BACKGROUND:

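### Read literally, one missing pain log or day-of-surgery report removes a participant from every secondary analysis, including outcomes she already provided

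*Combined protocol and SAP*

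**What the plan says.** The rule is one sentence in the combined protocol and SAP, under Withdrawal of Participants: "Participants would be excluded from secondary analyses if they did not complete their pain log or agree to report pain/satisfaction with TENS" on the day of surgery. It then protects the primary outcome: such participants "but would still be included in the primary analyses".

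The secondary outcomes listed under Objectives come from different sources.

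- **Pain at dilator exchange.** Under Procedures Involved, "a second set of cervical dilators is often placed 6 hours after first set in patients over 20 weeks gestation", and "Pain score on 100mm VAS will be recorded following this dilator placement as well as a secondary outcome".
- **Highest interval pain.** Under the same heading, "On the day of surgery participants will record their highest interval pain score on 100mm VAS".
- **Satisfaction.** A five-point Likert item, completed on a tablet. The VAS forms and the log are on paper.
- **Medication use.** A take-home log, with a second source: "They will return their completed log and bring pill bottles on the day of surgery to confirm medications used".
- **Clinic time.** Objectives lists "Amount of time (in minutes) spent in clinic following dilator insertion". It does not appear in the list of secondary outcomes under Study Endpoints or in the list of investigative procedures, and no section says how it is captured.

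The statistical text under Data Management and Confidentiality promises suitable methods for continuous or categorical outcomes. It defines no secondary analysis set and gives no missing-data method.

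**The concern.** The exclusion applies to the participant, not to the outcome. Any one of the triggers removes her, and what she is removed from is described only as the secondary analyses, set against the primary analyses as a group. An analyst following the sentence would discard values already in the database without a stated statistical reason.

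Two things are at stake. The first is precision in a trial of 70. The second is that the analysis set would be defined by behaviour after randomisation. The log covers pain, device use and medication. The sham unit passes no current, so a participant who feels nothing might plausibly stop using it and stop logging. If completion differs by arm and is related to pain, the rule carries that selection into outcomes, such as the exchange VAS, whose own recording does not depend on the log.

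**Working it through.** **Step 1: which recorded values the rule would discard.**

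| Secondary outcome | Source in the protocol | Lost under the literal rule although recorded? |
|---|---|---|
| Exchange VAS | VAS straight after the exchange, about 6 hours after first placement | Yes, if an exchange occurred and the log or day-of-surgery report is missing |
| Peak-pain VAS | Paper VAS on the day of surgery | Yes, if only the log is missing |
| Satisfaction | Tablet Likert item on the day of surgery | Yes, if only the log is missing |
| Medication use | Log, with pill bottles as confirmation | The bottle information is lost if bottles were brought without a log |
| Clinic time | Not stated | Only if it was captured |

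**Step 2: precision for peak pain.** There is no figure in the plan to reproduce, since it gives no precision or power for secondary outcomes. Inputs: 70 participants allocated 1:1, so 35 per arm (Procedures Involved), and SD 30 mm, which the plan states for its sample-size calculation and which is borrowed here for peak pain. The non-completion rate is an assumption. The plan's increase from 56 to 70 implies 1 − 56/70 = 20%, but it is an allowance for discontinuation and device misuse, not a log non-completion rate.

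Half-width of the 95% interval = t(0.975, 2n − 2) × 30 × √(2/n), with n per arm.

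- n = 35: 1.9955 × 7.171 = 14.3 mm.
- 10% lacking only the log, n = 31 (31.5 rounded down): 2.0003 × 7.620 = 15.2 mm.
- 20%, n = 28: 2.0049 × 8.018 = 16.1 mm, which is 16.1/14.3 = 1.12, or 12% wider.
- 30%, n = 24 (24.5 rounded down): 2.0129 × 8.660 = 17.4 mm.

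Each of these is a ceiling for its rate. It supposes that everyone without a log still gave a peak-pain VAS and that nobody else was missing one. If 20% lacked the log and half of those also gave no peak-pain VAS, about 31 per arm would have the value anyway. The rule would then widen the half-width only from 15.2 to 16.1 mm.

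**Step 3: how a rule with several triggers compounds.** Assume that the log, the day-of-surgery VAS and the satisfaction item are each missing independently at rate p. The literal rule keeps 70 × (1 − p)³. Outcome-by-outcome analysis keeps 70 × (1 − p) for each item.

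| p | Literal rule | Outcome by outcome |
|---|---|---|
| 5% | 60 | about 67 |
| 10% | 51 | 63 |
| 15% | 43 | about 60 |
| 20% | 36 | 56 |

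Independence is an assumption. Overlap between the items narrows the gap.

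**Step 4: possible bias.** Suppose there is no true effect and SD is 30 mm, and that those excluded are the top fraction r on a latent variable correlated ρ with pain. The mean of those retained shifts by −ρ × 30 × φ(z)/(1 − r), where z is the 1 − r normal quantile. The factor φ(z)/(1 − r) is 0.195 at r = 10%, 0.350 at 20% and 0.497 at 30%.

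- 10% versus 20% excluded by arm: (0.350 − 0.195) × 30 = 4.65 mm. Multiplied by ρ = 0.3 to 0.5, this gives about 1.4 to 2.3 mm.
- 10% versus 30%: (0.497 − 0.195) × 30 = 9.06 mm, giving about 2.7 to 4.5 mm.
- Equal exclusion in the two arms: zero under this model.

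None of these rates or correlations comes from the documents.

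**The case against.** The strongest reply is about intent. The triggers are themselves the sources of the log, peak-pain and satisfaction outcomes, so the authors may have meant only that a participant drops out of the analyses those items feed. That is possible, but it is not written, and no other section says it. If it is what was meant, the sentence still needs changing, because an analyst cannot recover that meaning from it.

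Several stronger claims are tempting, and the documents do not support them.

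- A reader might infer that recorded clinic times would certainly be lost. No section shows that they are recorded.
- A reader might treat 20% as the plan's own estimate of missing logs. It is a general discontinuation allowance made for the primary outcome.
- A reader might call the exchange comparison the worst affected. Exchange is described only as frequent beyond 20 weeks, and no gestational-age distribution is given, so neither the subgroup's size nor its loss can be worked out.
- A reader might conclude that every secondary result is biased. Bias needs completion to differ by arm and to be related to pain, and neither is shown. At 10% versus 20% exclusion the modelled bias is small beside the 15 mm that the plan cites as the minimum clinically significant difference.
- A reader might take the pill count as a full replacement for the log. Bottles are documented only as confirmation, they arrive at the same visit as the log, and a count of the prescribed drugs cannot be assumed to capture other analgesics.

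It also stands that the primary analysis is expressly protected from this rule and that the plan claims no power for secondary outcomes. These points limit the reach of the concern but do not remove it.

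**Conclusion.** The concern holds in limited form. As written, the rule discards observed secondary data: the exchange VAS where there was one, and the peak-pain VAS or satisfaction score of anyone missing only the log. The loss of precision depends on an unknown completion rate; the 12% widening at an assumed 20% is an upper limit for that rate. Selection bias is possible, of unknown size and direction. The change should be made because the rule is worse than a simple alternative that needs no extra data. It does not threaten the primary result.

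**What to change.** Replace the exclusion sentence under Withdrawal of Participants with: *Each secondary outcome is analysed, by assigned arm, in all randomised participants for whom that outcome was recorded.* Report the number missing by arm for each outcome.

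Where the log is missing, pill-bottle counts may be used as a sensitivity analysis for the prescribed drugs only. They should not be merged into the main medication analysis, which would mix two ways of measuring.

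The cost is a short protocol edit and denominators that differ between secondary outcomes. The change does not cure informative missingness within an outcome: those who give no peak-pain VAS may still differ from those who do, so the counts by arm should be read with that in mind.
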